#### 5.2 On-Treatment and post-treatment toxicity evaluation

All patients will be seen prior to each fraction of stereotactic body radiotherapy and their toxicity evaluated by physical examination. Subsequently, patients will be evaluated for toxicity one month later and then every 3 months. Toxicities will be scored by the NCI CTCAE version 4.0. Also see Section 6.0.

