#### 6.3 Follow up Interval

The patient will be followed post-treatment for 16 months, or until death unless otherwise indicated. Evaluation during the follow up interval will consist of the following activities:

- 6.3.1 Physical exam and vital signs at one, two, and three months post SBRT, five months post SBRT, and then every three months thereafter.
- 6.3.2 Monthly blood work to be done at a local laboratory starting 2 weeks following SBRT CBC, Diff with platelets, basic electrolytes, BUN, creatinine, t-bili, ALT, AST, GGTP, calcium, magnesium, and phosphorus. Bloodwork to be completed for at least the first six months.
- 6.3.3 CT or FDG-PET/CT scans (for consistency procedure done at screening/planning will continue in follow-up) at 8 weeks post-treatment and every 12 weeks thereafter for 12 months for assessment of response to therapy and monitoring.
- 6.3.4 Patients will follow up with their treating medical oncologist after SBRT, and if deemed appropriate, will be able to start systemic therapy 2 weeks after treatment.

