#### 7.0 Statistical Considerations

#### 7.1 Study Design/Endpoints

The primary objective of this study is to determine the Maximum Tolerated Dose (MTD) and safety of SBRT for liver metastasis using dose escalation. Dose escalation will be via the traditional "up and down" scheme indicated in the two tables below. The traditional up and down study design is a rule-based design which recruits up to 6 patients at each of the 3 dose levels. Patients in cohort(s) of 3 will be entered and the first cohort will be given the lowest dose. The detailed decision rule is in the two Tables below, where there are decisions corresponding to one or more dose limiting toxicities at any given dose level.

- The three dose levels are:
  - 50 Gy in 5 fractions (10 Gy/fx) delivered over a 2-week period.
  - 60 Gy in 5 fractions (12 Gy/fx) delivered over a 2-week period.
  - 75 Gy in 5 fractions (15 Gy/fx) delivered over a 2-week period.

Dose limiting toxicity (DLT) will be defined as any grade III stomach, bowel, liver, or spinal cord toxicity, or any grade IV toxicity as defined by the Radiation Therapy Oncology Group (RTOG). The monitoring and evaluation for dose escalation is referenced below in section 7.3.1. Cohorts of three patients each will be treated at a dose level. Only toxicities observed prior to 7 months after the last fraction of radiation will affect dose escalation.

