#### 7.3.1 Analysis of the primary endpoints

Baseline descriptive statistics on all evaluable patients will be provided for demographic variables (age, sex, race/ethnicity), ECOG performance status, disease stage and status at the screening and treatment regimens previously used.

The NCI Common Terminology Criteria for Adverse Events, version 4.0 (CTCAE v4.0) will be used to evaluate toxicity. We will consider a toxicity to be an adverse event that is possibly, probably or definitely related to treatment. The maximum grade of toxicity for each category of interest will be recorded for each patient and the summary results will be tabulated by category and grade. We will describe all DLTs and other serious (≥ Grade 3) adverse events on a patient-by-patient basis; descriptions will include dose level and any relevant baseline data. The monitoring and follow-up procedures are listed in detail in section 6.3.1 and 6.3.2. Specifically, patients will be seen at one, two, and three months post SBRT, five months post SBRT, and then every three months thereafter. They will undergo a comprehensive physical exam at each of

these visits. Monthly blood work will also be completed starting 2 weeks following SBRT - CBC, Diff with platelets, basic electrolytes, BUN, creatinine, t-bili, ALT, AST, GGTP, calcium, magnesium, and phosphorus. Bloodwork will be completed and reviewed for at least the first six months. All toxicity data gathered from these visits will be graded according to CTCAE v4.0. Statistics on the radiation dose and number of fractions received by patients will be tabulated.

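### The toxicity calendar tied to escalation has no examination between months 5 and 8, while only toxicities observed before month 7 count, so the DLT count can be too low; section 5.2 gives a different calendar

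*Combined protocol and SAP*

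**What the plan says.** All references are to the combined protocol and SAP.

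- **Section 5.2** says that after the treatment visits "patients will be evaluated for toxicity one month later and then every 3 months", then adds "Also see Section 6.0".
- **Section 6.3.1** requires "Physical exam and vital signs at one, two, and three months post SBRT, five months post SBRT, and then every three months thereafter". The schema in 6.6 marks the same months for history and examination (1, 2, 3, 5, 8, 11, 14). Its month 7 column is empty.
- **Section 6.3.2** requires monthly blood work from two weeks after treatment, including bilirubin, ALT, AST and GGTP: "Bloodwork to be completed for at least the first six months".
- **Section 7.1** defines a DLT as "any grade III stomach, bowel, liver, or spinal cord toxicity, or any grade IV toxicity". It sets the window, "Only toxicities observed prior to 7 months after the last fraction of radiation will affect dose escalation", and names the monitoring source: "The monitoring and evaluation for dose escalation is referenced below in section 7.3.1".
- **Section 7.3.1** completes the chain, "The monitoring and follow-up procedures are listed in detail in section 6.3.1 and 6.3.2", and restates those months.
- **Section 7.2** treats a patient without a DLT as evaluable after one DLT-free month.

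**The concern.** The primary objective is the maximum tolerated dose (MTD), and it rests on very small counts: 0 against 1 DLT in three patients, or 1 against 2 in six. One uncounted event can turn a decision to stop into a decision to escalate.

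Two features of the text bear on that count. First, the protocol contains two toxicity calendars. Second, the calendar linked to escalation places its last examination inside the window at month 5 and the next at month 8, after the window has closed. Because the cut-off turns on when a toxicity is observed, an event that starts in month 6 and is first found at the month 8 visit falls outside the escalation rule even though it began inside the window. Any error from this source runs one way, towards escalation.

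**Working it through.** **The plan's own figure.** Three dose levels with up to six patients each gives 3 × 6 = 18, which matches the maximum in 7.2. The plan states no operating characteristics for the design, so there is nothing further to reproduce.

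**The two calendars against a 7-month window.**

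| Source | Examination months | Strictly before month 7 | Time from last examination to month 7 |
|---|---|---|---|
| 5.2 | 1, 4, 7, 10 | 1, 4 | 3 of 7 months (43%) |
| 6.3.1, 7.3.1, schema | 1, 2, 3, 5, 8, 11, 14 | 1, 2, 3, 5 | 2 of 7 months (29%) |

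The 5.2 visit at month 7 falls on the boundary and is not before it. On the second calendar, required blood work runs to month 6, so the stretch with neither an examination nor a required blood test is about 1 of 7 months (14%).

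**Chance of escalating from one of the lower two levels.** Under the escalation table in 7.1, a level is passed with 0 DLTs in 3 patients, or with 1 in the first 3 and 0 in the next 3. With DLT probability p and q = 1 − p:

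P(escalate) = q³ + 3pq² × q³

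If a share m of DLTs is not observed before month 7, p is replaced by p(1 − m). The documents give neither p nor the timing of DLTs, so both are assumptions. Onset is taken as uniform over 7 months, and each decision is assumed to use complete 7-month follow-up.

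- m = 0: every DLT is counted.
- m = 1/7: half of the events starting in months 5 to 7 are missed, for example if everything up to month 6 is found.
- m = 2/7: nothing that starts after the month 5 examination is found in time.

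For p = 0.33:

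- m = 0: 0.67³ + 3(0.33)(0.67²)(0.67³) = 0.301 + 0.134 = 0.434
- m = 1/7: p becomes 0.283, giving 0.369 + 0.161 = 0.530
- m = 2/7: p becomes 0.236, giving 0.446 + 0.184 = 0.631

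For other true rates:

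| True DLT rate | m = 0 | m = 1/7 | m = 2/7 |
|---|---|---|---|
| 20% | 0.709 | 0.770 | 0.828 |
| 30% | 0.494 | 0.584 | 0.678 |
| 33% | 0.434 | 0.530 | 0.631 |
| 40% | 0.309 | 0.410 | 0.524 |

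**Top level.** Here 0 of 3 leads to three more patients, so the condition is at most 1 DLT in 6: q⁶ + 6pq⁵. At p = 0.33 this is 0.090 + 0.267 = 0.36. With m = 2/7 it is 0.199 + 0.369 = 0.57. The level differs from the table, but the direction and rough size of the shift are the same.

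**Whole trial.** With assumed true rates of 10%, 20% and 40% at the three levels, simulation of both decision tables (60,000 runs per case) declares the top level the MTD in 14.9% of trials for m = 0, 23.8% for m = 1/7 and 35.5% for m = 2/7.

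**The case against.** The strongest reply is that the calendar for escalation is not in doubt and that other channels cover the gap.

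- Section 7.1 leads to 7.3.1 and from there to 6.3.1 and 6.3.2, and 5.2 itself defers to section 6. The conflict in 5.2 is therefore mainly editorial. This stands. A reader might infer that the 5.2 calendar causes the undercount. It does not, and adopting it would lengthen the unexamined stretch from 2 months to 3.
- Liver tests continue monthly to at least month 6 and are reviewed and graded (6.3.2, 7.3.1). Serious events are to be phoned in within 24 hours (8.2.1), a board reviews toxicity and escalation monthly (8.1), and patients also see their medical oncologist (6.3.4). Many DLTs are severe enough to bring a patient to care between visits. This stands in large part. However, the reporting and review routes act only on events already known to staff, and the blood panel does not directly test for stomach, bowel or spinal cord toxicity.
- The probabilities depend on uniform onset. Section 5.2.1 lists several serious effects as short-term and calls long-term effects less likely, which points to earlier onset and a smaller loss. This stands. The figure for m = 2/7 is a ceiling only if uniform onset is granted.
- No passage requires 7 months of follow-up before a cohort decision. A patient without a DLT is evaluable at one month (7.2), and 18 patients at 6 a year fill the planned 3 years with no explicit waiting time. If decisions come earlier, 0.43 is the wrong comparator and the gap between months 5 and 8 is not the main reason late events go uncounted. This also stands, and it is a second passage to reconcile.

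**Conclusion.** The point holds in a limited form. The calendars conflict. On the one tied to escalation, the wording of the cut-off excludes a DLT that begins before month 7 but is first found at month 8. That follows from the text without any assumption, and it can only lower the DLT count. The events at risk are mainly non-laboratory DLTs not reported before month 7, and laboratory DLTs that arise after the last required test.

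The size is unknown. Under uniform onset and complete 7-month follow-up, the chance of escalating from a lower level at a true 33% DLT rate lies between 0.43 (no loss) and 0.63 (nothing detected after month 5), with 0.53 for a loss of 1/7. These figures are a sensitivity range and do not estimate how this trial will behave.

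A reader might go further and infer that late DLTs are in fact lost and that escalation is too easy. The documents do not show this: they give no onset times, and the between-visit channels would catch many such events. Nor do they say why 7 months was chosen, so it cannot be claimed that the window was set to capture late events.

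**What to change.** 1. Reconcile 5.2 with 6.3.1, 7.3.1 and the schema, so that one toxicity calendar applies.
2. In 7.1, define the 7-month cut-off by the date of toxicity onset instead of the date of observation.
3. State how a DLT found after an escalation decision updates the count at its dose level and the MTD. The change to onset is incomplete without this rule.
4. Align an existing toxicity assessment and blood test with the end of the window, so that its last part is covered.
5. Reconcile the 7-month window in 7.1 with the one-month evaluability definition in 7.2, and state how much follow-up a cohort decision requires.

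The direct cost is protocol wording and one re-timed or added assessment with blood tests per patient. If item 5 leads to longer follow-up before each decision, the accrual period in 7.2 would need to be checked as well.

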## 5.2.1 Stereotactic Body Radiation Therapy Related-Toxicity

Implantation of a liver marker: The side effects of implantation will be similar to the needle biopsy of liver tumor and stent placement. These include but are not limited to tumor seeding, foreign body, infection, bleeding, pain at local area, and dislocation of the marker.

SBRT: Short-term side effects include but not limited to skin reaction, local hair loss, fatigue, abdominal pain, nausea, vomiting, diarrhea, increasing liver function abnormality, GI bleeding or perforation which may require surgical intervention. Long term side effects are less likely to occur but if they do occur are more likely to be permanent. They include local hair loss, liver function abnormality, diarrhea, small bowel obstruction which may require surgical intervention, spinal cord injury which could result in paralysis, and kidney function abnormality.

#### 5.2.2 CT and FDG-PET/CT

The subject will be exposed to radiation associated with the FDG-PET/CT and/or CT scans performed to assess the liver metastases and their response to therapy. FDG-PET/CT and CT scans are routinely performed as standard-of-care for tumor staging and to monitor response to therapy, and the radiation dose associated with these diagnostic scans are felt to represent minimal risk.

Adverse reactions to the administration of the FDG being used for the PET/CT scans are not expected. However, as with the administration of any drug, the possibility of an adverse event cannot be totally excluded. The subject will be monitored for adverse events, and a physician and emergency drugs and equipment will be available in the scanning area should a reaction occur.

Claustrophobia: Possible anxiety, claustrophobia, and/or temporary discomfort may occur as a result of being placed in the scanning devices. Subjects will be monitored and removed from the scanner if required

#### 6.0 STUDY EVALUATIONS

#### 6.1 Pretreatment Evaluation

The following tests/procedures will be performed in order to ascertain subject eligibility within 28 days prior to registration unless otherwise specified. Some of the standard of care testing may be performed before the research consenting process and if in the window, results will be used for screening, but no testing exclusively ordered for research will be done before the consent is signed.

- 6.1.1 Signed informed consent
- 6.1.2 Medical history
- 6.1.3 Physical examination, including Karnofsky Performance Status or ECOG performance status and vital signs.
- 6.1.4 Subject body weight and height taken within 14 days of the registration.
- 6.1.6 Histologic and/morphologic confirmation of diagnosis, and disease status/staging at entry.
- 6.1.7 CBC including: WBC with complete differential, platelets, RBC, hemoglobin, hematocrit, within 30 days prior to registration.
- 6.1.8 Blood chemistries including BUN, creatinine, total bilirubin, AST, ALT, alkaline phosphatase, sodium, potassium, calcium, phosphorus, chloride, magnesium within 30 days of registration.
- 6.1.9 Urine or blood HCG test for female subjects of child-bearing potential (women who are not at least 1 year post-menopause or who have not undergone a surgical sterilization procedure) within 14 days prior to registration. Female subjects of child-bearing potential will be instructed to use contraception from the time of the screening pregnancy test until study completion.
- 6.1.10 FDG-PET/CT (or if insurance does not allow for a PET, then a contrast enhanced CT) of the abdomen and pelvis within 45 days prior to registration.
- 6.1.11 Patient will be discussed by a multi-disciplinary team involving surgical oncology, medical oncology, and radiation oncology to reinforce that surgery is the current standard of care for such patients

#### 6.2 Evaluation during treatment

The patient will be carefully followed while on active treatment and post-treatment for 16 months, or until death. Evaluation during treatment will consist of the following activities:

- 6.2.1 Administration of stereotactic body radiation therapy.
- 6.2.2 Interim medical history and physical examination at baseline and prior to each radiation therapy treatment.

#### 6.3 Follow up Interval

The patient will be followed post-treatment for 16 months, or until death unless otherwise indicated. Evaluation during the follow up interval will consist of the following activities:

- 6.3.1 Physical exam and vital signs at one, two, and three months post SBRT, five months post SBRT, and then every three months thereafter.
- 6.3.2 Monthly blood work to be done at a local laboratory starting 2 weeks following SBRT CBC, Diff with platelets, basic electrolytes, BUN, creatinine, t-bili, ALT, AST, GGTP, calcium, magnesium, and phosphorus. Bloodwork to be completed for at least the first six months.
- 6.3.3 CT or FDG-PET/CT scans (for consistency procedure done at screening/planning will continue in follow-up) at 8 weeks post-treatment and every 12 weeks thereafter for 12 months for assessment of response to therapy and monitoring.
- 6.3.4 Patients will follow up with their treating medical oncologist after SBRT, and if deemed appropriate, will be able to start systemic therapy 2 weeks after treatment.

#### 6.4 Study procedures

#### 6.4.1 PET/CT Imaging

Patients will be required to fast for at least 4 to 6 hours prior to the FDG-PET/CT imaging procedure. Prior to injection of [F]-fluorodeoxyglucose ([F]-FDG), a 1 ml blood sample (1/3 teaspoonful) will be taken to measure the patient's blood glucose level. After the injection of 10-15 mCi of [F]-FDG and an approximate 45 minute wait allowing for tracer incorporation, a CT scan will be performed for attenuation correction and anatomical correlation on the General Electric Discovery ST PET/CT (GE Medical Systems, Waukesha, WI) scanner. The CT scanner portion of the GE ST consists of a multi-detector spiral CT scanner. CT scans will be acquired as diagnostic quality CT, after the patient receives 900 ml Gastroview orally and 125 ml Optiray 350 intravenously (I.V.) through an automated injector. This will be followed by a whole body emission PET scan. The [F]-FDG is being used in this study in accordance with the current FDA regulations addressing radioactive drugs for use in PET procedures. The total scan duration, including a spiral CT scan of the same axial extent as the FDG-PET, will not exceed 60 min. A CT scan will be acquired over the same axial length as the FDG-PET scan.

#### 6.5 Objective criteria for defining response

#### 6.5.1 Definition of Response

#### 6.5.1.1 Clinical Benefit Response

Clinical benefit response is a measure of clinical improvement based on analgesic consumption, pain intensity, performance status and weight change.

A patient is considered a clinical benefit responder if either:

a. The patient shows a  $\geq$  50% reduction in pain intensity or analgesic consumption OR

b. Improvement in performance status (Appendix IV) of  $\geq$  20 points for a period of at least four consecutive weeks, without showing any sustained worsening in any of the other parameters (sustained worsening was defined as four consecutive weeks with either any increase in pain intensity or analgesic consumption or a  $\geq$  20 point decline in performance status

OR

c. The patient is stable on all of the aforementioned parameters, and shows a marked, sustained weight gain ( $\geq 7\%$  increase maintained for  $\geq 4$  weeks) not due to fluid accumulation

#### 6.5.1.2 Tumor Response on CT (RECIST)

Measurable Disease Response: CTEP's RECIST guidelines will be followed. A quick reference to the RECIST guidelines can be downloaded at the following URL: http://ctep.info.nih.gov/Policies/WordDocs/RCSTF.PH2TEMPF.doc. (Appendix II) Patients enrolled in this study must have a measurable liver metastasis which is defined as lesions that can be accurately measured in at least one dimension: [longest diameter to be recorded] on the CT scan.

The same method of assessment and the same technique should be used to characterize each identified & reported lesion at baseline & during follow-up.

F	Parameters to Measure Response Outcome:			
1 Clinical examination				
2	CT scan			
3	FDG-PET/CT scan			

Taking into account the measurement of the longest diameter only for those lesions with size response, response criteria are defined as:

- 1. Complete Response (CR): the disappearance of a lesion.
- 2. Near Complete Response (NCR): at least an 80% decrease in the longest diameter of a lesion, taking as reference the longest diameter recorded since the treatment started.
- 3. Partial Response (PR): at least a 30% decrease in the longest diameter of a lesion, taking as reference the longest diameter recorded since the treatment started.
- 4. Progressive Disease (PD): at least a 25% increase in the longest diameter of a lesion, taking as reference the longest diameter recorded since the treatment started.
- 5. Stable Disease (SD): neither sufficient shrinkage to qualify for partial response nor sufficient increase to qualify for progressive disease, taking as reference the longest diameter since the treatment started.

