#### Efficacy data collected

The following evaluations will be performed to assess the efficacy of stereotactic body radiation therapy:

- Locoregional control
- Objective tumor response (by RECIST and EORTC 1999 criteria)
- Radiological assessment using FDG-PET/CT to evaluate local control compared to CT
- Quality of life assessment, FACT-HEP score, a validated measure of HRQL in hepatobiliary disease.

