#### Baseline documentation of "Target" and "Non-Target" lesions

- All measurable lesions up to a maximum of five lesions per organ and 10 lesions in total, representative of all involved organs should be identified as target lesions and recorded and measured at baseline.
- Target lesions should be selected on the basis of their size (lesions with the longest diameter) and their suitability for accurate repeated measurements (either by imaging techniques or clinically).
- A sum of the longest diameter (LD) for all target lesions will be calculated and reported as the baseline sum LD. The baseline sum LD will be used as reference by which to characterize the objective tumor.
- All other lesions (or sites of disease) should be identified as non-target lesions and should also be recorded at baseline. Measurements of these lesions are not required, but the presence or absence of each should be noted throughout follow-up.

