#### Response Criteria

## **Evaluation of target lesions**

* Complete Response (CR):	Disappearance of all target lesions
* Partial Response (PR):	At least a 30% decrease in the sum of the LD of target lesions, taking as reference the baseline sum LD
* Progressive Disease (PD):	At least a 20% increase in the sum of the LD of target lesions, taking as reference the smallest sum LD recorded since the treatment started or the appearance of one or more new lesions
* Stable Disease (SD):	Neither sufficient shrinkage to qualify for PR nor sufficient increase to qualify for PD, taking as reference the smallest sum LD since the treatment started
	Evaluation of non-target lesions

* Complete Response	Disappearance of all non-target lesions and normalization of tumor				
(CR):	marker level				
* Incomplete	Persistence of one or more non-target lesion(s) or/and maintenance of				
Response/	tumor marker level above the normal limits				
Stable Disease (SD):					
* Progressive Disease	Appearance of one or more new lesions and/or unequivocal				
(PD): progression of existing non-target lesions (1)					

(1) Although a clear progression of "non target" lesions only is exceptional, in such circumstances, the opinion of the treating physician should prevail and the progression status should be confirmed later on by the review panel (or study chair).

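### Section 6.5.1.2 measures CT partial and near-complete response from the longest diameter since treatment started, while Appendix II, which it says it follows, measures partial response from the pre-treatment baseline

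*Combined protocol and SAP*

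**What the plan says.** Section 6.5.1.2 opens by saying that "CTEP's RECIST guidelines will be followed" and points to Appendix II. Its own list of categories then uses a different reference:

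- NCR (item 2): "at least an 80% decrease in the longest diameter of a lesion, taking as reference the longest diameter recorded since the treatment started".
- PR (item 3): "at least a 30% decrease in the longest diameter of a lesion, taking as reference the longest diameter recorded since the treatment started".
- Progressive disease, PD (item 4): "at least a 25% increase in the longest diameter of a lesion, taking as reference the longest diameter recorded since the treatment started".
- SD (item 5): neither enough shrinkage nor enough growth, against the same longest diameter.

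Appendix II defines PR as "At least a 30% decrease in the sum of the LD of target lesions, taking as reference the baseline sum LD". Its section on baseline documentation says "The baseline sum LD will be used as reference by which to characterize the objective tumor". For PD it uses a 20% increase, "taking as reference the smallest sum LD recorded since the treatment started".

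Section 6.1.10 places the screening scan within 45 days before registration, and therefore before treatment. Section 6.3.3 places the first follow-up scan at 8 weeks after treatment, with further scans every 12 weeks.

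The Protocol Summary lists objective tumour response by RECIST among the efficacy data. Section 6.5.1.3 sends tumours that are not FDG-avid to 6.5.1.2 for response assessment.

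**The concern.** Two readers can each follow the protocol faithfully and classify the same lesion differently, because the body text and the appendix it invokes name different reference scans.

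The body text also has two possible readings. Under the literal one, a diameter recorded since treatment started cannot be the screening diameter. The 8-week scan becomes the first reference, and shrinkage already reached by then never counts. Under the inclusive one, baseline belongs to the set and the reference is the largest diameter seen so far, so enlargement or an upward measurement error makes a later 30% decrease easier to reach.

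At stake is the objective response tabulation by dose group. The trial treats no more than 18 evaluable patients, so one reclassified patient shifts an overall rate by 1/18 = 5.6 percentage points. For non-FDG-avid tumours, and for patients followed by CT alone, section 6.5.1.2 is the only imaging response measure.

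**Working it through.** The plan gives no figure to reproduce here. The check scores example lesions under each rule, then asks how often an unchanging lesion would read as PR. All diameters and measurement SDs below are assumptions, since the documents give none.

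**Inputs.** PR threshold −30%, NCR threshold −80%, PD threshold +25% (6.5.1.2) or +20% (Appendix II). Scans at weeks 8, 20, 32 and 44 (6.3.3).

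**Rules.** Change = diameter ÷ reference − 1, where the PR reference is:

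- literal: the largest earlier follow-up diameter (at week 8, the scan itself);
- inclusive: the largest of baseline and earlier follow-up diameters;
- Appendix II: baseline.

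**Example lesions** (mm; baseline, then four scans)

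| Record | Literal | Inclusive | Appendix II |
|---|---|---|---|
| 50, 20, 20, 20, 20 | 0% at every scan: SD throughout | −60%: PR throughout | −60%: PR throughout |
| 40, 26, 22, 20, 20 | 0, −15, −23, −23%: never PR | −35, −45, −50, −50%: PR throughout | same as inclusive |
| 30, 45, 30, 30, 30 | SD, then −33%: PR | +50%: PD, then −33%: PR | +50%: PD, then 0%: never PR |
| 30, 37, 45, 30, 30 | SD, SD, then −33%: PR | +23% SD, +22% SD, then −33%: PR | PD, PD, then 0%: never PR |

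**Swelling needed for a false PR.** A return exactly to baseline reads as −30% from the peak only if the peak is at least 1/0.7 − 1 = 42.9% above baseline. For NCR it is 1/0.2 − 1 = 400%, which is not realistic. Under the inclusive reading, an abrupt rise of 25% or more is scored PD first. The fourth record avoids that because each step is below 25% (37/30 = +23.3%, 45/37 = +21.6%).

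**Unchanging lesion.** Five log-normal measurements (baseline and four follow-ups), 400,000 simulated lesions. A PR reading is a follow-up diameter at or below 70% of the reference.

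| Assumed SD | Any PR reading, baseline reference | Any PR reading, running maximum including baseline |
|---|---|---|
| 8% | 0.3% | 0.7% |
| 10% | 2.1% | 4.8% |
| 12% | 5.7% | 12.9% |
| 15% | 13.5% | 28.5% |

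Appendix II requires PR to be confirmed at least 4 weeks later. On this schedule that means the next scan. Requiring two consecutive PR scans at 10% SD gives 0.16% versus 0.33% per lesion. For at least one of three lesions, 1 − (1 − 0.0016)³ = 0.5% versus 1 − (1 − 0.0033)³ = 1.0%. At 12% SD the three-lesion figures are 2.0% versus 4.1%.

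**The case against.** The strongest reply is that the literal reading is strained. It compares the first follow-up scan with itself, so neither response nor progression could be called at 8 weeks. The section invokes RECIST and asks for the same technique at baseline and follow-up, so an assessor would probably include baseline. Both early-responder records then score correctly. That narrows the problem but leaves the running maximum and the conflict with Appendix II.

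Several stronger conclusions are tempting and are not supported:

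- **That the plan's response rate or its McNemar test is biased.** Section 6.5.1.5 counts SD, PR and CR together in both local control and Local Response Rate. Moving a lesion between SD and PR changes neither, nor a McNemar test (7.3.2) using that definition.
- **That CT and PET responses are measured from different starting points.** In 6.5.1.3 only the progression item names the baseline scan. The partial metabolic response item names no reference scan.
- **That false PR becomes common.** The unconfirmed figures for at least one of three lesions look large (about 6% versus 14% at 10% SD), but confirmation reduces them to 0.5% versus 1.0%.
- **That any lesion that swells and settles becomes a responder.** A record such as 40, 52, 36 mm gives 36/52 − 1 = −31%, but 52/40 = +30% at week 8 is PD under Appendix II and under the inclusive reading. Appendix II ends best response at progression. Only the literal reading gives PR with no earlier PD.
- **That NCR is missing from 6.5.1.5.** An 80% decrease already meets the PR threshold.

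**Conclusion.** The contradiction is real and should be corrected, but its reach is limited. It affects objective tumour response by RECIST and the PR/NCR/SD tabulations, including those for non-FDG-avid tumours. It does not touch the primary endpoint, local control or Local Response Rate.

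Under the literal reading the error is large for an individual lesion: any response complete by 8 weeks is lost. Under the inclusive reading it is small. The running maximum roughly doubles the chance of a false PR reading across assumed SDs of 8% to 15%, but at 10% SD the confirmed chance stays below 1% per lesion. Real swelling matters only when it is about 43% or more before a return to baseline, and mainly when it builds up in steps below 25%.

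The PD item has the same reference problem, and that item can affect local control and local failure. For example, 50, 25, 35, 45, 50 mm is never PD under the inclusive reading, but is PD from the second scan under Appendix II (35/25 = +40%). This is a separate consequence of the same phrase and is best settled together with it.

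**What to change.** In section 6.5.1.2, items 2 and 3, and for the shrinkage limb of item 5, replace the reference with *the longest diameter on the pre-treatment baseline scan*. This matches the reference that Appendix II uses for PR. Changing items 2 and 3 alone would leave SD judging shrinkage against a different scan.

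In the same edit, reconcile the PD reference and threshold in item 4 with Appendix II. Because disease progression is also a removal criterion in 8.1.1, the investigators should make that choice explicitly. The text should also say whether response is scored per lesion, as in 6.5.1.2, or on the sum of diameters, as in Appendix II.

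No change to 6.5.1.5 is needed for NCR. The cost is wording only: no added scans, measurements or patients. The edit should be made before responses are read, so that the reference is not chosen after seeing the data.
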